8.2 GENERAL CONSIDERATION

The statistical analysis of the data will be performed using SAS version 9.3 or higher or another industry standard statistical software package. Continuous variables will be summarized using descriptive statistics, specifically the mean, median, standard deviation, minimum and maximum. Categorical variables will be summarized by frequencies and percentages. The summaries will be provided for the LAL eyes and Control eyes separately. For continuous outcomes, the difference between the two eyes of the same subject will be calculated and summarized by using descriptive statistics for continuous outcomes.

Unless otherwise specified, all p-values will be two-sided for a two-sided significance level of 0.05 (or one-sided for a one-sided significance level of 0.025) and all confidence intervals will be two-sided at 95% confidence level. Safety analyses will be performed on eyes in which IOL implants are attempted.

A detailed statistical analysis plan (SAP) will be developed and finalized prior to the locking of the database for this study.

8.3 BASELINE CHARACTERISTICS

Baseline characteristics (such as age, gender, race, and pre-operative pathology) will be summarized descriptively for subjects with the LAL implantation attempted and for subjects implanted with LAL in one eye and Control lens in the other eye by means and standard deviations or by counts and percentages, as appropriate. They will also be stratified by the study site in order to assess the similarity of these baseline characteristics among the study sites.

Baseline characteristics will be listed for subjects with a successful LAL implantation but a failed Control lens implantation, if they exist.

8.4 POPULATIONS FOR ANALYSIS

8.4.1 SAFETY POPULATION

The safety population consists of any subject who has signed the informed consent and has the LAL procedure attempted which is defined as the point at which the lens makes contact with the eye. This population will be used for the safety. No imputation will be performed.

8.4.2 Intent to Treat (ITT) Population

The intent to treat (ITT) population contains all enrolled subjects who have been randomized and are intent to have the LAL and Control lens procedures. However, since the ITT subjects that exit from the study before the LAL procedure will not have clinical data regarding either safety or effectiveness for both LAL and control lenses, these subjects will be excluded from the statistical analyses. These subjects include those reported with surgical complications before implantation of LAL is attempted and exited from the study.

8.4.3 FULL ANALYSIS SET (FAS)

The Full Analysis Set (FAS) is a subset of the ITT which consists of the ITT subjects that have the LAL implanted in one eye and the Control lens in the other eye. The primary analyses for the primary and secondary effectiveness endpoints will be based on the FAS. For the FAS subjects that do not have the Postop Month 6 data, the missing MRCYL, MRSE, and UCDVA will be assumed to the same for their two eyes in the primary analyses. Different imputations will be included in the sensitivity analyses described in Section 8.5.2 below and in the SAP of this study protocol.

8.4.4 PER-PROTOCOL (PP) POPULATION

The per-protocol population is a subset of the FAS and is comprised of the FAS subjects who have complete LDD treatment in the LAL eyes, have Postop Month 6 data, and do not have any major protocol deviations. The PP population will be used for supportive effectiveness analyses. Major protocol deviations will include those deviations that may impact subject safety, affect the integrity of study data and/or affect subject willingness to participate in the study, such as implantation, adjustment and lock-in procedures that are not performed as specified in the protocol and/or Operator's manual.

8.4.5 BEST CASE COHORT

The best case cohort is defined as the LAL implanted eyes with no preoperative pathology (pseudoexfoliation, glaucoma, previous glaucoma filtering surgery, poor pupil dilation, previous uveitis, previous retinal detachment, diabetic retinopathy, macular degeneration, and amblyopia). Per ISO 11979-7:2014 (E), the BCDVA outcomes will be summarized for this cohort as well.

The binomial distribution will be used for the following statistical hypotheses as described in Section 8.1 for the LAL-eye in FAS:

H0: $p \ge 0.925$ versus Ha: p < 0.925 with a one-side significance level of 0.05.

8.5.2 SECONDARY/SENSITIVITY ANALYSES FOR THE PRIMARY AND SECONDARY EFFECTIVENESS ENDPOINTS

If there are FAS subjects with missing Postop Month 6 data, the analyses described in Section 8.5.1 will be performed for the FAS using the following imputations for missing MRCYL, MRSE, logMAR UCDVA, and logMAR BCDVA data:

- Baseline value (i.e., a non-responder approach) for continuous parameters and non-responder assumption (BCDVA worse than 20/40) for binary outcome
- Best cases: The best outcome of all eyes for the LAL eyes with missing data and the worst outcome of all eyes for the control eyes with missing data.
- Worst cases: The best outcome of all eyes for the control eyes with missing data and the worst outcome of all eyes for the LAL eyes with missing data
- Mean of observed value at Postop Month 6 of the same eye group in the FAS.
- Mean of observed value at Postop Month 6 of the different eye group in the FAS (i.e. using mean of the LAL group to impute the missing value in the Control group and using mean of the Control group to impute the missing value in the LAL group)
- Last observed carry forward

For the mean logMAR BCDVA, a value of ≤ 0.3 is equivalent to a Snellen value of 20/40. The same analyses will also be performed based on the PP population defined in Section 7.4.3.

Per ISO 11979-7: 2014 (E), the analysis for the outcome of BCDVA of 20/40 or better at Postop Month 6 will also be performed on the observed data of the Best-Case cohort. It should be noted that the performance goal of the percent of Best-Case cohort with BCDVA of 20/40 or better is 96.7%, instead of 92.5%.

8.5.3 COVARIATES AND SUBGROUP ANALYSES

The following covariates will be evaluated for their effect on the primary effectiveness endpoints based on the FAS population with the imputation for the missing data used for the primary analyses:

- Age group (based on observed quartiles)
- Gender (male and female)
- Race (White and non-White)
- Ethnicity (Hispanic-Latino and not Hispanic-Latino)
- Study site

For Δ MRCYL, Δ |MRSE|, and Δ UCDVA at Postop Month 6, two-sample t-test or one-way ANOVA (for covariates with more than two sub-categories) will be used to evaluate the effect of the covariate. For the percentage of LAL-eyes with BCDVA of 20/40 or better at Month 6, Fisher's exact test will be performed to evaluate the covariate effect on the outcome.

A p-value of 0.15 will be used for evaluating the possible covariate effects. It should be noted that the subgroups of these covariates will be re-examined and may be re-categorized or eliminated due to small sample size (if there are < 10 subjects within each subgroup).

8.5.4 ADDITIONAL EFFECTIVENESS ANALYSES

The following effectiveness outcomes will be summarized descriptively based on the observed data for the LAL and Control eyes separately. The analyses on the difference between the LAL-eye and Control eye will only include the subjects implanted with LAL in one eye and control lens in the other eye.

Manifest Cylinder (MRCYL)

The MRCYL and MRCYL change from Postop Week 3 will be presented beginning at Postop Week 3 using descriptive statistics for continuous outcomes. The number and percent of eyes with a MRCYL of \leq 0.25 D, 0.50, 0.75 D, 1.0 D, 1.25 D, 1.5 D, 1.75, and \geq 2.0 D will be reported for each visit. The Δ MRCYL will also be summarized at each visit by using the descriptive statistics for continuous outcomes.

In addition, for the LAL eyes, MRCYL at Postop Month 6 will be summarized descriptively (mean, standard deviation, minimum/maximum, quartiles) by the Postop Week 3 MRCYL (using 1.00 D bins), by the Postop Week 3 MRSE (using 1.00 D bins) and by the preoperative Kcyl (using 0.25 D bins). The same analyses will be performed for the control eyes. The observed outcomes will be clinically compared. It should be noted that two eyes of the same subjects can be in different Postop Week-3 MRCYL groups, different Postop Week-3 MRSE groups, or different preoperative Kcyl groups.

Cylinder Correction Accuracy

For eyes without cylindrical treatment, the intended cylinder correct will be assumed to be 0. The accuracy of cylinder correction to intended target within 0.50 D and 1.00 D will be reported beginning at Postop Months 1-2 for the LAL eyes and for the Control eyes. Additionally, the deviation of the achieved adjustment from the attempted adjustment will be summarized by the descriptive statistics for continuous outcomes.

The analyses for the LAL eyes described above will also be stratified by the Postop Week 3 MRCYL (using 1.00 D bins) and the Postop Week 3 MRSE (using 1.00 D bins).

Vector Difference

Vector differences between the intended cylinder change and the achieved cylinder change will be calculated and summarized descriptively. In eyes for which no cylinder adjustment was attempted, the intended change will be considered zero and the entire change from Week 3 will be treated as an error. The summary will be provided for the LAL-eye and control eye separately. The difference in the vector length between the two eyes (= LAL-eye minus Control-eye) will be calculated for each subject and summarized descriptively at each visit.

Additionally, for the LAL eyes, a scatter plot will be presented showing the vector length of the change between the vector cylinder at the Postop Week 3 and Postop Month 6 visit as a

function of intended cylinder change and as a function of intended MRSE change. In order to evaluate the MRSE treatment effect on the cylindrical outcome, a regression analysis on the vector length with the intended cylinder correction and intended MRSE correction as independent factors will be performed. The regression residual will be checked for the model fitting.

Refractive Cylinder Stability

Refractive cylinder stability will be presented for consistent cohort and eyes with two consecutive visits. The following statistics will be calculated.

- Percentage of eyes that achieve change of ≤ 1.00 D of refractive cylinder;
- Percentage of eyes that achieve change of \leq 0.50 D of refractive cylinder;
- Mean MRCYL change between two visits and the corresponding 95% confidence interval, mean change per month, and mean change per year

MRSE

MRSE and change in MRSE from Postop Week 3 will be summarized by the descriptive statistics for continuous outcomes (such as mean and standard deviation) for each visit. The number and percent of eyes with an MRSE of $\leq \pm 0.25$ D, ± 0.50 , ± 0.75 D, ± 1.0 D, and ± 2.0 D will be reported for each visit. For each subject, the difference in the MRSE between two eyes (= LAL-eye – Control-eye) at Postop Week 3 and beyond will be calculated and the difference will be summarized by using descriptive statistics for continuous variables.

In addition, for the LAL eyes, the MRSE at Postop Month 6 will be summarized descriptively (mean, standard deviation, minimum/maximum, quartiles, number and percent of eyes in the outcome categories described above) by the Postop Week 3 MRSE (using 1.00 D bins), by the Postop Week 3 MRSE (using 1.00 D bins), and by the pre-operative Kcyl (using 0.25 D bins). The same analyses will be performed for the control eyes. The observed outcomes will be clinically compared. It should be noted that two eyes of the same subjects can be in different Postop Week-3 MRCYL groups, different Postop Week-3 MRSE groups, or different preoperative Kcyl groups.

Additionally, for the LAL eyes, a scatter plot will be presented showing the change in MRSE between the Postop Week 3 and 6 month visit as a function of intended MRSE change and intended cylinder change. For evaluating the cylindrical treatment effect on the MRSE outcome, a regression analysis on MRSE change with the intended MRSE change and intended cylinder change as independent factors will be performed. The regression residuals will be used to validate the fitted model.

Accuracy of MRSE

The number and percent of eyes with a MRSE correction compared to the intended target within 0.25 D, 0.50 D, 0.75 D, 1.0 D, 1.25 D, 1.5 D, 1.75 D, and ≥ 2.0 D will be reported at each visit beginning at Postop Months 1-2. For eyes without MRSE correction, 0.00 D will be used for the intended target. Additionally, the deviation of the achieved adjustment from the attempted adjustment will be summarized by the descriptive statistics for continuous outcomes.

The analyses for the LAL eyes described above will also be stratified by the Postop Week 3 MRCYL (using 1.00 D bins) and the Postop Week 3 MRSE (using 1.00 D bins).

Absolute MRSE

Absolute MRSE and change in absolute MRSE from Postop Week 3 will be summarized by the descriptive statistics for continuous outcomes (such as mean and standard deviation) for each visit. The $\Delta |\text{MRSE}|$ at Postop Week 3 and beyond will also be summarized by using descriptive statistics for continuous variables.

Additionally, for the LAL eyes, the absolute MRSE outcomes at Postop Month 6 will be stratified by signed MRSE at Postop Week 3 (using 0.25 D bins) and summarized descriptively (mean, standard deviation, minimum/maximum, quartiles). The mean percent reduction and the number in each bin will also be provided.

Refractive MRSE stability

The refractive stable point will be determined based on the five criteria described in Section F.3 of ANSI Z80.11-2012 document as follows:

- At least 95% of the treated eyes have a change ≤1.00 D of MRSE between the two refractions:
- The mean rate of change in MRSE, as determined by a paired analysis, is ≤ 0.5 D per year (0.04 D/month) over the same time period;
- The mean rate of change of MRSE decreases monotonically over time, with a projected asymptote of zero or a rate of change attributable to normal aging;
- The 95% confidence interval for mean rate of change includes zero or a rate of change attributable to normal aging.

The MRSE change between the following post-adjustment visit intervals will be presented.

- From Postop Months 1-2 to Postop Month 3
- From Postop Month 3 to Postop Month 6

Defocus Equivalent (DEQ)

The DEQ will be summarized descriptively at Postop Week 3 and beginning at Postop Months 1-2. The number and percent of eyes with DEQ \leq 0.5 D and 1.0 D will also be summarized at the corresponding visit.

Autorefraction

Autorefraction sphere, cylinder, and spherical equivalent will be summarized descriptively at each visit.

Since, for the LAL eyes, the light adjustment will be based on the manifest refraction, the following change in auto-refraction cylinder (Cyl) and reduction in auto-refraction spherical equivalent (SE) will be calculated for each LAL eye:

Change in Cyl = (Postop Month 6 autorefraction Cyl – Postop Week 3 MRCYL),

Change in SE = (Postop Month 6 autorefraction SE – Postop Week 3 MRSE)

The change in cylinder and the change in the spherical equivalent will be summarized descriptively by mean, standard deviation, median, minimum, and maximum.

UCDVA

UCDVA will be presented with the number and percent of eyes who fall into each category of UCDVA at each visit (e.g. 20/20 or better, 20/25 or better, 20/32 or better, etc.). The logMAR UCDVA will be summarized by descriptive statistics for continuous outcomes for each visit. Change in UCDVA from Postop Week 3 will be presented at each visit as categorical outcomes of "increase in 15 letters or more", "Increase in 10-14 letters", "Increase in 5-9 letters", "Decrease in 10-14 letters", and "Decrease in 15 letters or more". The change in logMAR UCDVA from Postop Week 3 will also be presented.

The outcome of within-subject Δ UCDVA will be presented at each visit as categorical outcomes of "LAL 15 letters or more better", "LAL 10-14 letters better", "LAL 5-9 letters better", "LAL 1-4 letters better", "LAL = Control", "Control 1-4 letters better", "Control 5-9 letters better", "Control 10-14 letters better", and "Control 15 letters or more better". The descriptive statistics for continuous outcomes will also be calculated for the within-subject Δ UCDVA.

BCDVA

BCDVA will be presented with the number and percent of eyes that fall into each category of BCDVA at each visit (e.g. 20/20 or better, 20/25 or better, 20/32 or better, etc.). The logMAR BCDVA at each visit will also be presented by using descriptive statistics for continuous variables. The analyses will be repeated for the Best Case Cohort.

[figure not shown]
Per ISO 11979-7 2014 (E), the BCDVA categorical summaries described above will also be stratified by the following covariates and clinical outcomes for the LAL eyes.

- Age group (based on observed quartiles)
- With versus without ISO cumulative AEs
- With versus without ISO persistent AEs
- With versus without preoperative ocular pathology
- Study site

The analyses above may be reconsidered due to the observed stratification. For example, if no subjects are reported with any ISO persistent AEs, then the BCDVA by ISO persistent AEs will not be performed.

For the LAL and Control eyes that cannot achieve BCDVA of 20/40 or better at the last available visit, the BCDVA data listing along with the reported possible reasons of failing to achieve 20/40 or better will be provided.

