6.1 INCLUSION CRITERIA

- Must sign a written Informed Consent form and be willing to undergo cataract surgery for the bilateral implantation of an intraocular lens (IOL).
- Between the ages of 40 and 80 inclusive on the day the cataract surgery is performed.
- Preoperative keratometric cylinder ≤ 2.00 in both eyes.
- History of Laser-Assisted In Situ Keratomileusis (LASIK), Photorefractive Keratectomy (PRK), Laser-Assisted Subepithelial Keratomileusis (LASEK), Epi-LASIK, or Epi-LASEK more than 1 year prior in both eyes.
- Cataract causing reduction in best corrected distance visual acuity (BCDVA) to a level of 20/40 or worse with or without a glare source in both eyes.
- Best corrected distance visual acuity projected (by clinical estimate based upon past ocular history and retinal exam) to be 20/20 or better after cataract removal and IOL implantation in both eyes.
- Clear intraocular media other than cataract in both eyes.
- Willing and able to comply with the requirements for study specific procedures and visits.
- Average dilated pupil diameter of ≥ 7.0 mm in both eyes.
- Able to complete a written questionnaire in English.
- Requires an IOL power within the range available for both the LAL and the Sensar AR40e.

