Per the previous PMA clinical study, the standard deviation of logMAR UCDVA at Postop Month 6 is 0.11 D for the LAL group and 0.17 for the control group. Assuming the UCDVA at Postop Month 6 of the two eyes of the same subject are independent, the estimated standard deviation of Δ UCDVA is 0.21 (= square-root of the sum of 0.11² and 0.17²). Again, a larger standard deviation, 0.32 (\sim 1.5 × 0.21) is used for the sample size calculation. Based on the one-sided one-sample t-test (i.e. paired t-test) with a significance level of 0.0125, a sample size of 60 subjects can provide a statistical power of 90% if the true μ_{Δ UCDVA is -0.15 (i.e. 1.5 lines).

2. UCDVA at Postop Month 6 for subjects with keratometric cylinder (Kcyl) < 0.75 D at the preoperative examination in both eyes

H0: $\mu_{\Delta UCDVA_L} = 0$ versus Ha: $\mu_{\Delta UCDVA_L} < 0$ with a one-side significance level of 0.0125, where $\mu_{\Delta UCDVA_L}$ is the mean $\Delta UCDVA$ at Postop Month 6 for subjects with Kcyl < 0.75 D (low cylinder) at the preoperative examination in both eyes.

Based on the same assumptions discussed in the Section above, the required sample size for the analysis is 60 subjects. It is estimated that about 60% of the subjects at Postop

Month 6 will have a preoperative KCyl of < 0.75 D. Therefore, $100 (= 60 \div 60\%)$ bilateral subjects at Postop Month 6 are needed for this endpoint

Study Sample Size

Based on the sample size calculation for the primary and secondary primary effectiveness endpoints above, a sample size of 100 bilateral subjects at Postop Month 6 will be sufficient for the study. With a drop-out rate of at most 10% within the 6-month follow-up period and possible postponed LDD treatment after postoperative 6 months, up to 110 bilateral subjects should be implanted with LAL in one eye and Control lens in the other eye. Considering possible intraoperative complications that prevent the LAL implantation, it is determined that the study should attempt implantation in up to 120 eligible bilateral subjects in order to have at least 100 bilateral subjects at Postop Month 6.

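### The regression on whether MRSE treatment affects cylinder (8.5.4) most naturally takes the length of total cylinder change as its response, which dilutes induced cylinder in treated eyes; name the error-vector length instead and fix the MRSE coding

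*Combined protocol and SAP*

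**What the plan says.** All of this is in section 8.5.4 under Vector Difference. The first paragraph sets up an error vector: "Vector differences between the intended cylinder change and the achieved cylinder change will be calculated and summarized descriptively". For eyes with no cylinder adjustment, "the intended change will be considered zero and the entire change from Week 3 will be treated as an error". The same paragraph then plans a within-subject comparison: "The difference in the vector length between the two eyes (= LAL-eye minus Control-eye) will be calculated for each subject".

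The second paragraph turns to LAL eyes. It plans a scatter plot "showing the vector length of the change between the vector cylinder at the Postop Week 3 and Postop Month 6 visit", against intended cylinder change and intended MRSE change. The regression follows at once. Its purpose is stated as "In order to evaluate the MRSE treatment effect on the cylindrical outcome", and its specification is "a regression analysis on the vector length with the intended cylinder correction and intended MRSE correction as independent factors will be performed".

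The MRSE part of 8.5.4 has a matching pair, a scatter plot of MRSE change followed by a regression whose response is explicitly MRSE change. No planned model relates the error vector to intended MRSE.

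**The concern.** The regression is meant to show whether spherical treatment leaves unwanted cylinder behind. That quantity is the difference between the cylinder change achieved and the change intended. The length of the whole change is something else, because it is dominated by the treatment that was meant to happen. The parallel MRSE regression escapes the problem because MRSE change is a signed scalar. Cylinder change is a vector, and taking its length discards direction.

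If the response is total change, a flat slope on intended MRSE could be read as evidence that spherical treatment induces no cylinder, when the response was poorly placed to show it. Manifest cylinder at Month 6 is a primary endpoint, so readers will care about the answer even though nothing formal depends on this model.

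**Working it through.** **Which response is meant.** The regression sentence says only vector length. The sentence just before it uses that phrase for the Week 3 to Month 6 change, in the same eyes and with the same two predictors. The MRSE counterpart regresses the change. Both point to total change. Against this, the first paragraph uses the phrase after describing the error vector. Total change is therefore the natural reading, not a certain one.

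**Geometry (no noise or sample-size assumption).** Work in double-angle coordinates. Let d be the intended change, i the induced cylinder and θ the angle between them.

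- Length of total change: |d + i| = √(d² + i² + 2di·cos θ) ≈ d + i·cos θ + (i²/2d)·sin² θ.
- Averaged over a random θ, the cosine term vanishes and the excess over d is about i²/(4d).
- Length of error: |achieved − intended| = i, whatever d and θ are.

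With i = 0.25 D, averaged over all axes:

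| Intended d | i²/(4d) | Exact rise in length of change | Length of error |
|---|---|---|---|
| 0 | – | 0.250 D | 0.25 D |
| 0.5 D | 0.031 | 0.032 D | 0.25 D |
| 1.0 D | 0.016 | 0.016 D | 0.25 D |
| 2.0 D | 0.008 | 0.008 D | 0.25 D |

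At fixed axes with d = 1.0 and i = 0.25, the length of change moves by +0.25 D (parallel), √(1 + 0.0625) − 1 = +0.031 D (orthogonal) and −0.25 D (opposed).

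**Axis error.** A full-size change 15° off axis is 30° off in double-angle terms. Its error is 2·sin 15° = 0.52 of the intended cylinder, yet its length equals d, so it scores as no deviation.

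**Size in a regression.** The plan states no power or effect for this model, so there is no figure to reproduce. From the documents come n = 100 (section 8.1: "a sample size of 100 bilateral subjects at Postop Month 6 will be sufficient for the study") and a guide to the upper end of cylinder (section 6.1: "Preoperative keratometric cylinder ≤ 2.00 in both eyes"). The rest is assumed: treated eyes 0.5 to 2.0 D intended, intended MRSE SD 0.7 D entered as magnitude, 0.3 D induced per D at a random axis, and least squares with the plan's two predictors, tested at two-sided 0.05.

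| Eyes without cylinder treatment | Noise SD per component | Power, length of change | Power, length of error |
|---|---|---|---|
| 0% | 0.25 D | about 14% | about 86% |
| 30% | 0.25 D | about 23% | about 87% |
| 60% | 0.25 D | about 46% | about 86% |
| 30% | 0.15 D | about 45% | about 100% |
| 60% | 0.15 D | about 81% | about 100% |

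With no induced cylinder, both responses reject about 5 to 6% of the time.

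**Other axes (30% untreated, noise 0.25 D).** With parallel induction, power is about 99% for length of change and 85 to 87% for error length. With opposed induction, the slope is about −0.15 D/D for length of change and about +0.15 D/D for error length, so growing error appears as a smaller change.

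**Predictor coding (same settings, random axis).** If intended MRSE enters with its sign and induction is the same for myopic and hyperopic corrections, the mean slope is near zero for both responses and each rejects about 11% of the time.

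**The case against.** The strongest reply has five parts.

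- **Wording.** The first paragraph ties the same phrase to the error vector, so the plan may already intend the right response. This stands as a limit: one cannot say that the plan definitely uses total change. The same clarifying sentence is needed either way.
- **Assumptions.** The loss depends on axis, noise and the share of untreated eyes, and the documents give none of these for this analysis. This stands. Parallel induction favours total change. Untreated eyes lose nothing, because there the two responses are identical; at 80% untreated and noise SD 0.15 D, power for total change is 97%. Section 8.1 expects about 60% of subjects to have keratometric cylinder below 0.75 D in both eyes, but that is not the share of eyes left without cylinder treatment.
- **Effect size.** At 0.15 D per D (30% untreated, noise 0.25 D) power is about 9% and 19%, so neither response would detect much. This stands.
- **Coding.** Changing the response alone recovers nothing if intended MRSE is signed and the effect is symmetric. This stands, and the fix has to cover it.
- **Other coverage.** Month 6 cylinder and cylinder correction accuracy are summarised by Week 3 MRSE in 1.00 D bins, and the error vector is summarised on its own. These help, but they are descriptive and coarse, and none relates the error vector to intended MRSE.

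A reader might infer that the planned regression cannot see induced cylinder, or will mostly report no effect. The documents do not support that: they fix neither the axis of induced cylinder nor the share of treated eyes, and untreated eyes carry the full signal.

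**Conclusion.** The point holds in limited form. On its most natural reading, the regression uses a response ill suited to its stated purpose. In cylinder-treated eyes it registers randomly or orthogonally oriented induced cylinder only to second order (0.016 D for 0.25 D induced at 1.0 D intended), ignores axis error, and reverses sign under opposed induction. The geometric result needs no noise or sample-size assumption. The power figures do: across the random-axis settings tabulated at 0.3 D per D, length of change has about 14% to 81% power and error length about 86% to 100%, with MRSE entered as magnitude in both.

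It would be wrong to infer that the loss applies to every eye or axis, or that it is cured however intended MRSE is coded. Nor is any efficacy conclusion at risk: this is an additional analysis with no decision rule, and the primary MRCYL comparison does not use it. It is worth correcting because the correction is nearly free.

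**What to change.** In the Vector Difference part of 8.5.4, and in the detailed SAP that section 8.2 says will be finalised before database lock:

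1. Name the length of the intended-minus-achieved cylinder vector as the regression response.
2. Add that length to the scatter plot, against intended cylinder change and intended MRSE change.
3. State that intended MRSE enters as magnitude, or as separate myopic and hyperopic terms.
4. Keep the length of the Week 3 to Month 6 change as a descriptive plot against intended cylinder.

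The cost is two or three sentences. The error vector is already to be calculated, so no new data are needed, and no endpoint, sample size or significance level changes.
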